#### **10.4.2 Potential Drug Induced Liver Injury**

A summary of the number and percentage of subjects who met PDILI criteria at any visit and at Visit 13 will be summarized overall, and by age cohort for all subjects and by infusion group. Results from local laboratory should be included, if applicable. Subjects who meet one or more of the criteria for potential drug-induced liver injury (PDILI) at Visit 1 or Visit 13 will be listed. The listing will display only visits for which at least one of the criteria for PDILI (see [Appendix 12.3](#)) was fulfilled for a given subject, and will display all results obtained at that visit for the specified variables associated with PDILI. Potential Hy's law cases will be flagged.

All potential drug-induced liver injury (PDILI) events require immediate action, testing, and monitoring (see [Appendix 12.3](#)). The measurements and additional information required for the assessment of PDILI events when there is a reasonable possibility that they may have been caused by the IMP are included but not limited to those listed in laboratory measurements.

Additional PDILI information will also be listed. If specific PDILI information collected separately is matching to the entries in the standard eCRF pages collected for all subjects, the specific PDILI information will be added to the corresponding listing for the standard eCRF information. For information collected on top (eg, family history of PDILI, lifestyle) a new listing will be generated.

Suspected hepatic events will be listed.

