10.2.1 Evaluation of PDILI

The PDILI IMP discontinuation criteria for this study are provided in Section 6.3.1, with the accompanying required follow-up investigation and monitoring detailed below. All PDILI events must be reported as an AE and reported to the study site and Sponsor within 24 hours of learning

of their occurrence. Any PDILI event that meets the criterion for potential Hy's Law must be reported as an AE of special interest (see Section 10.1.1.3), and, if applicable, also reported as an SAE (see Section 10.1.2.3).

Evaluation of PDILI consists of the diagnostic testing and continued monitoring included in Table 10-3 (specific tests dependent on laboratory results and corresponding symptoms) and consultation with a local hepatologist (if applicable; discussed in Section 10.2.1.1). The local hepatologist is the expert usually consulted by the treating physician for assessment and management of potential hepatic disease. This would usually be a hepatologist, but may be a gastroenterologist. Additional investigation and monitoring may be required and adapted based on the diagnosis after the cause of the liver injury/abnormality is confirmed (details in Section 10.2.1.4).

The results of all monitoring, including laboratory testing and other testing, should be made available to the study site and Sponsor.

All initial tests resulting in abnormal hepatic laboratory values need to be repeated, but appropriate medical action must not be delayed waiting for the repeat result.

If tests are done locally for more rapid results, a concurrent sample should also be sent to the central laboratory whenever possible. Medical care decisions are to be made initially using the most rapidly available results and a conservative approach must be taken if the results from the 2 laboratory tests are significantly different. Data from the local and central laboratory are to be recorded on the applicable CRF pages.

When IMP is discontinued, all concomitant medications and herbal supplements that are not medically necessary should also be discontinued. In these cases, the Investigator should also consider dose reduction for medically necessary concomitant medication and consider changing any medically required concomitant medication known to be hepatotoxic to a suitable alternative.

Rechallenge with a substance potentially causing drug-induced liver injury is dangerous, may be fatal, and must not occur.

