##### 2.2.2.2 Other safety variables

- 12-lead ECG values before, during, and after each iv BRV administration
- Blood pressure (BP), pulse rate, respiratory rate (RR), and temperature values before, during, and after each iv BRV administration
- Clinical laboratory parameters (hematology, chemistry, and endocrinology) pre and post treatment
- Urinalysis parameters pre and post treatment

Post treatment parameters will be only available for subjects who down titrate and perform Visit 13 assessments.

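### The SAP's PDILI listing admits only subjects who qualify at Visit 1 or Visit 13, while the PDILI table counts qualifying values from any visit, so a child who qualifies only at another draw is missing from the listing and its Hy's Law flag

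*SAP*

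**What the plan says.** SAP 10.4.2 defines two PDILI outputs in one paragraph.

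- **Summary table.** It gives the number and percentage of subjects "who met PDILI criteria at any visit and at Visit 13", overall, by age cohort and by infusion group. The next sentence adds: "Results from local laboratory should be included, if applicable".
- **Listing.** Subjects who meet at least one criterion "at Visit 1 or Visit 13 will be listed". For a listed subject the display rule is: "The listing will display only visits for which at least one of the criteria for PDILI" was met, with all PDILI-related results from each such visit. Then comes: "Potential Hy's law cases will be flagged".

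SAP Appendix 12.3 gives the criteria. Every row starts at ALT or AST of at least 3xULN, and the Hy's Law footnote adds total bilirubin of at least 2xULN.

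On data availability, SAP 2.2.2.2 states: "Post treatment parameters will be only available for subjects who down titrate and perform Visit 13 assessments". Protocol 10.2.1 requires further draws once a liver value is abnormal: "All initial tests resulting in abnormal hepatic laboratory values need to be repeated".

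**The concern.** The table and the listing that should support it select subjects by different rules. The table looks at all visits and accepts local results. The listing looks at two visits, one of them before any iv dose. A child who qualifies only at some other draw would appear as a number in the table with no corresponding line in the PDILI listing.

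That listing is the only planned output that combines the SAP's PDILI criteria, the associated liver results at the qualifying visit and, by its place in the paragraph, the Hy's Law flag. In a study this small, a liver case would be read individually. A reader who goes from the count to the PDILI listing would not find it there.

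**Working it through.** No figure in the plan needs reproducing. The check sets the rules side by side and follows each kind of case through them.

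**Which visits have scheduled chemistry.** Protocol Table 5-1 schedules it at Visit 1 only. Table 5-4 schedules it at Visit 13, for subjects not continuing into the long-term study.

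**Can a treated child qualify at Visit 1?** Hardly. Exclusion 14 bars ALT or AST above 1.5xULN. A result up to 25% above that limit may be repeated once, so the highest first value that could still lead to entry on retest is 1.5 x 1.25 = 1.875xULN. The lowest entry point in Appendix 12.3 is 3xULN. Barring an eligibility deviation, this route is closed.

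**Who has a Visit 13?** Protocol 8.6 gives it to subjects who down-titrate and to those who withdraw without needing down-titration. Protocol 6.3 also says subjects who withdraw without down-titration should complete it. Children who move to the long-term study do not have it. For them, neither of the listing's two visits offers a realistic post-infusion route in.

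**Are draws at other times foreseen?** Yes.
- Protocol 8.8 allows additional assessments at Unscheduled Visits.
- Protocol 10.2.1 and Table 10-3 require repeat liver tests and, for PDILI, monitoring at least twice a week.
- Protocol 10.2.1 foresees local testing when results are needed quickly, whereas routine safety chemistry goes to the central laboratory (Protocol 10.2). The local-laboratory sentence in SAP 10.4.2 therefore points to draws outside the routine schedule.

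**Following the cases through SAP 10.4.2:**

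| Criterion met at | Any-visit table | PDILI listing |
|---|---|---|
| Visit 1 or Visit 13 | counted | listed |
| Visit 13 and another draw | counted | listed, both visits displayed |
| Another draw only | counted, on the natural reading | not listed, so not flagged there |

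The third row is the gap.

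**Do other outputs carry the third-row case?** They carry it, but without the SAP's PDILI classification.
- The laboratory listing (SAP 10.4.1) shows the values, but its PCST indicator is confined to values at Visit 13.
- Additional laboratory tests have their own listing (SAP 10.4.1).
- Suspected hepatic events and additional PDILI information are listed (SAP 10.4.2), with no PDILI or Hy's Law criterion stated for either.
- The adverse event listings (SAP 10.2.2) show whether an event is of special interest. Protocol 10.2.1 requires a potential Hy's Law event to be reported that way. That mark uses a different definition: Protocol 10.1.1.3 also requires that ALP is not at or above 2xULN and that there is no alternative explanation. The footnote in SAP Appendix 12.3 uses only ALT or AST plus bilirubin.

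**What one unmatched case would look like.** With about 50 children treated, 1/50 = 2.0% overall. In a cohort of about 12 it is 1/12 = 8.3%. In half a cohort, about 6 children on one infusion duration, it is 1/6 = 16.7%. These show what a single case does to the table. They are not an expected frequency.

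**The case against.** The strongest reply is that nothing is hidden. Protocol 10.2.1 makes every PDILI event an adverse event and a potential Hy's Law event one of special interest. Those events, all chemistry results and any suspected hepatic event are listed without a Visit 1 or Visit 13 limit. This stands. A reader might infer that such a case would be neither listed nor flagged anywhere, and the documents do not support that.

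Second, the limit selects subjects, not displayed visits. Once a child qualifies at Visit 13, any follow-up draw that meets a criterion is displayed too. Monitoring triggered by a scheduled Visit 13 value therefore starts from a child already in the listing. This also stands. The gap needs a child whose only qualifying value lies outside the two visits.

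Third, SAP 3.1 confines summary tables to visits foreseen by the protocol. If the any-visit count meant only scheduled chemistry visits, the table and the listing would agree. This does not remove the defect. PDILI repeats and monitoring are required by the protocol and so are foreseen, and the local-laboratory sentence favours the wider reading. On the narrow reading, the case would be in neither PDILI output. SAP 3.1 also treats listings as broader than tables, and here the listing is the narrower of the two.

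Fourth, the Hy's Law sentence has no visit limit of its own, and its tie to the listing is inferred from position. That is correct, and it is a further reason to state its scope.

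**Conclusion.** The selection rule for the PDILI listing is wrong as written, in a minor way. On the natural reading of the any-visit count, a child who qualifies only at a draw other than Visit 1 or Visit 13 is counted in the table but left out of the PDILI listing and the flag attached to it.

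The gap mainly concerns children who continue into the long-term study. It is tempting to extend it to every child who stops without down-titration, and SAP 2.2.2.2 taken alone would suggest that. Protocol 6.3 and 8.6 say otherwise: children who withdraw should complete Visit 13.

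The size cannot be put as a number of cases. The documents give no PDILI rate and do not say what share of children will continue into the long-term study. No estimate and no data collection are affected. What is affected is whether the PDILI table can be traced to its own listing. The conclusion rests on two readings: that any visit includes unscheduled visits, and that the flag belongs to the listing it follows.

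**What to change.** In SAP 10.4.2:

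1. Change the listing's entry rule from Visit 1 or Visit 13 to any scheduled or unscheduled visit, with results from the central or a local laboratory. The existing display rule can stay.
2. State that the Hy's Law flag applies to every subject admitted under that rule.
3. State that the any-visit count in the summary table includes unscheduled visits, so that the subjects in the table and in the listing agree.

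The cost is one changed phrase, two clarifying statements and a change to one listing program. No new data are needed.

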## **10.5 Vital signs, physical findings, and other observations related to safety**

### **10.5.1 Vital signs and body weight**

Vital signs (systolic blood pressure [SBP], diastolic blood pressure [DBP], respiratory rate [RR], temperature, pulse rate) and body weight will be collected according to the protocol schedule of study assessments.

Observed values of body weight will be summarized for each visit by infusion duration, and by subject group for the SS-iv.

Observed values of SBP, DBP, RR, temperature and pulse rate will be summarized for each time point (as defined in [Section 4.8](#)) within each visit. Change from Baseline for SBP, DBP, RR, temperature, and pulse rate will be summarized for all post-Baseline time points within each visit. Tables will be provided overall and by age cohort, for all subjects and by infusion duration, and by subject group for the SS-iv. Observed values for SBP, DBP, RR, temperature, and pulse rate at each timepoint will be plotted as a line for each subject in line graphs by visit (Visit 1 to 3, then for each visit individually i.e. Visit 4, 5, etc), age cohort and infusion duration. Abnormal values defined by the PCST criteria will be marked using symbols.

Vital signs PCS/PCST definitions are located in [Appendix 12.2.4](#). Vital signs PCST events (i.e. Treatment-emergent vital signs PCS) are defined as events which started on or after the first BRV medication taken during the EP0065 study that meet PCS criteria. Subjects who began the study on BRV treatment (OLB and RxB subjects) will be assumed to have taken BRV treatment on the first day of screening. Therefore, timing of a PCS being treatment emergent (i.e. a PCST) varies by subject group: all PCS are treatment emergent for RxB and OLB subjects; all PCS on or after the IOB Treatment Period are treatment emergent for IOB subjects; all PCS on or after the iv PK Period are treatment emergent for IIB subjects.

All vital signs measurements (scheduled and unscheduled) which are taken after the first BRV medication during the EP0065 study will be assessed to determine if they meet PCST criteria. The number and percentage of subjects that meet the criteria for any PCST value, a high PCST value and a low PCST value at each timepoint and visit will be presented for each variable individually overall and by age cohort for all subjects and by infusion duration. A separate summary will be presented by country of enrollment (Hungary and rest of the World) for all subjects and by infusion duration. Percentages will be relative to the number of subjects with a value at each corresponding timepoint or visit.

The number of occurrences of each unique PCST type will be tabulated by timepoint within each visit for each subject, and include relevant criteria: gender, age, race, timepoint, visit, subject group and infusion duration. In addition, the number of subjects with at least one PCST will be displayed for each age cohort.

A subject data listing of all vital sign values will be presented. The listing will contain columns indicating which values met the criteria for PCS and PCST. All body weight values will be listed and will contain a column indicating the PCS and PCST criteria.

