### 10.4 Clinical laboratory evaluations

#### 10.4.1 Hematology, Chemistry and Urinalysis Parameters

Laboratory values will be collected according to the protocol schedule of study assessments. In case a laboratory test is repeated at one visit, the latest measurement will be used for summary

tables. For continuous laboratory variables (including hematology and chemistry) summary statistics of Baseline values, Visit 13 values, and change from Baseline will be presented overall and by age cohort, for all subjects, and by infusion duration at each study visit for the SS-iv. For categorical urinalysis laboratory variables summary statistics of Visit 1 and Visit 13 values will be presented overall and by age cohort, for all subjects, and by infusion duration for the SS-iv.

Shifts from Baseline to Visit 13 based on the normal range (ie, low, normal, high, and missing) for each hematology, and chemistry lab parameter will be presented for subjects who have a Baseline and Visit 13 measurement overall and by age cohort, for all subjects and by infusion duration for the SS-iv. Shifts from Baseline to Visit 13 based on the categorization of each urinalysis lab parameter will be presented for subjects who had done a Baseline and Visit 13 measurement, overall and by age cohort, for all subjects and by infusion duration for the SS-iv.

The number and percentage of subjects with possibly clinically significant treatment-emergent (PCST) for each laboratory variable (i.e. PCST low value, PCST high value) for hematology, biochemistry (including Thyroxine (T4)) and urinalysis will be summarized overall and by age cohort, for all subjects, and by infusion duration. The criteria for a laboratory value to be PCST is defined in [Appendix 12.2](#), but note, only laboratory variables that meet PCST criteria at Visit 13, but not Baseline will be considered as PCST.

The number of occurrences of each unique PCST type will be tabulated by timepoint within each visit within each subject, and include relevant criterion: gender, age, race, timepoint, visit, subject group and infusion duration. In addition, the number of subjects with at least one PCST will be displayed for each age cohort.

The following listings will be provided: all laboratory results of clinical chemistry, hematology, urinalysis including an indicator as to which met the criteria for PCST. A separate listing will contain all additional laboratory tests performed and sample takes.

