## 10.5.2 Electrocardiograms (ECGs)

Standard 12-lead ECGs (heart rate, RR-interval, PQ/PR interval, QRS duration, QT interval, QTcB interval) will be performed throughout the study, according to the protocol schedule of assessments. The QTcF interval will be calculated using the following formula:

$$QTcF = \frac{QT}{\sqrt[3]{RR}}$$

Observed values of ECG parameters will be summarized for each timepoint within each visit. Change from Baseline for ECG parameters will be summarized for all post-Baseline timepoints within each visit. Tables will be provided overall, and by age cohort for all subjects, and by infusion duration, and subject subgroup for the SS-iv. Values for all ECG parameters at each timepoint will be plotted as a line for each subject in line graphs by visit (Visit 1 to 3, then for each visit individually i.e. Visit 4, 5 etc.), age cohort, and infusion duration. Abnormal values are defined by the PCS/PCST criteria (see [Appendix 12.2.5](#)) and will be displayed using symbols. ECG PCST events (i.e. Treatment-emergent ECG PCS) are defined as events which started on or after the first BRV medication taken during the EP0065 study that meet PCS criteria. In subjects who began the study on BRV treatment (OLB and RxB subjects), they will be assumed to have taken BRV treatment on the first day of screening. Therefore, timing of a PCS being treatment emergent (i.e. a PCST) varies by subject group: all PCS are treatment emergent for RxB and OLB subjects; all PCS on or after the IOB Treatment Period are treatment emergent for IOB subjects; all PCS on or after the iv PK Period are treatment emergent for IIB subjects.

All ECG parameter measurements (scheduled and unscheduled) which are taken after the first BRV medication during the EP0065 study will be assessed to determine if they meet PCST criteria. The number and percentage of subjects that meet the criteria for PCST at each timepoint and visit will be presented for each variable individually overall and by age cohort for all subjects and by infusion duration. A separate summary will be presented by country of enrollment (Hungary and rest of the World) for all subjects and by infusion duration. Percentages will be relative to the number of subjects with a value at each corresponding timepoint or visit.

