The number and percentage of subjects with normal, abnormal not clinically significant, and abnormal clinically significant ECG findings, as assessed by the investigator, will be summarized for all timepoints within visits overall and by age cohort for all subjects and by infusion duration.

Shift tables will display the number and percentage of subjects having the same and different ECG finding (normal/abnormal not clinically significant/abnormal clinically significant) at each post-iv timepoint compared to their pre-iv ECG finding in the same visit, for all subjects and by age cohort, by infusion duration. Therefore, for subjects on bolus the shift from pre-iv BRV to ≤2, 5, 15, 30, 60 minutes and 2 hr after initiation of iv BRV result will be displayed, and for subjects on 15 minutes infusion the shift from pre-iv BRV to 5, 10, 15, 30, 60 minutes and 2 hr after initiation of iv BRV result will be displayed.

A subject data listing will be provided for 12-lead ECG results and will contain a column indicating the PCS and PCST criteria if a subject had abnormal ECG value. A separate listing will be provided, displaying the 12-lead ECG findings including a record of whether each finding was clinically significant or not.

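### Vital-sign and ECG PCST is defined by timing alone, so an unchanged pre-existing abnormality can be counted as treatment-emergent after the infusion

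*SAP*

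**What the plan says.** SAP 10.5.1 first defines vital-sign PCST as "events which started on or after the first BRV medication taken during the EP0065 study that meet PCS criteria". It then sets the start of the window by subject group. For children who enter on BRV, "all PCS are treatment emergent for RxB and OLB subjects". For IOB subjects the window opens with the IOB Treatment Period, and for IIB subjects with the iv PK Period. All scheduled and unscheduled measurements "which are taken after the first BRV medication during the EP0065 study will be assessed to determine if they meet PCST criteria". SAP 10.5.2 repeats the same rule for ECG, and the version 4.0 change log records the OLB/RxB rule as intended.

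Laboratory PCST is defined differently in SAP 10.4.1: "only laboratory variables that meet PCST criteria at Visit 13, but not Baseline will be considered as PCST".

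For both vital signs and ECG, PCST percentages are planned at each time point and visit. For vital signs only, SAP 10.5.1 adds two displays. One is a per-subject table: "The number of occurrences of each unique PCST type will be tabulated by timepoint within each visit for each subject". The other is a summary count: "the number of subjects with at least one PCST will be displayed for each age cohort".

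SAP 3.4 sets Baseline as the last assessment before the first iv infusion. Protocol 12.4.1.2 allows, without requiring, shift tables of post-iv against pre-iv status for each bolus or infusion.

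**The concern.** The study asks whether iv BRV is safe in children, and SAP 2.3 names iv BRV as the study medication. A reader will take a treatment-emergent percentage in a post-infusion cell to mean that children became abnormal after the infusion. Under this definition the cell also includes children who were abnormal beforehand and did not change. That holds even for IIB children, who have had no oral BRV in the study to justify a wider window.

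At stake is how a descriptive summary of non-primary safety variables is read, in cells so small that one child visibly moves the percentage. Blood pressure deserves particular care, because Protocol Amendment 1 added monitoring, on the DMC's recommendation, to investigate blood pressure changes.

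**Working it through.** **1. Is there an onset condition?** The opening definition could be read as requiring a new onset. The sentences after it remove that reading: they class all PCS values in the window as treatment-emergent and have every measurement assessed. Neither section refers to Baseline status.

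**2. Which criteria can an unchanged value meet?** Children are enrolled under 16 years and stay at most 68 days, so the under-17 rows of SAP 12.2.4 and 12.2.5 apply.

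| Variable | Form of the criterion | Value equal to Baseline | Flagged now | Flagged if absence at Baseline were required |
|---|---|---|---|---|
| Systolic BP, 3 to <12 y | absolute (>140 mmHg on the high side) | 142 mmHg | yes | no |
| QTc | ≥440 ms or ≥15% increase | 445 ms | yes | no |
| ECG heart rate, 3 to <12 y | ≥130 bpm and an increase of ≥20 bpm | 135 bpm | no | no |

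Diastolic BP, pulse, respiratory rate and temperature also have absolute limits. PR and QRS have the same limit-or-increase form as QTc. Uncorrected QT has no criterion under 17 years. Low BP is largely guarded, because Protocol 5.2 withholds the infusion while the pre-dose BP is low PCS. Amendment 1 added that hold while the study was running, so children treated earlier may not have been covered.

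**3. How many cells does one child affect?** SAP 4.8 gives 7 ECG and BP time points per infusion: 1 before and 6 after. For pulse, respiratory rate and temperature there are 5 after, since only BP is taken at 2 hours. A child who stays beyond the limit is PCST at every one of these.

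**4. Size per cell.** Each cohort has about 12 children, about half per infusion duration.

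- Cell of 6: 1/6 = 16.7 percentage points.
- Cohort of 12: 1/12 = 8.3 percentage points.

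**5. How often might it happen?** The documents give no prevalence. Assume a share p of children has a stable PCS value of one variable. The expected number is n × p, and the chance of at least one is 1 − (1 − p)^n.

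| Assumed p | Expected in 50 | At least one in 6 | At least one in 12 |
|---|---|---|---|
| 5% | 2.5 | 26% | 46% |
| 10% | 5 | 47% | 72% |
| 20% | 10 | 74% | 93% |

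Exclusion criterion 10 (a clinically relevant ECG abnormality in the Investigator's opinion) makes the upper end less likely for ECG. It does not use the PCS limits.

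**6. Pooling in the vital-sign count.** An OLB or RxB child with one infusion has 2 BP readings before iv (Visit 1 and pre-infusion) and 6 after. Assume a chance r per reading, independent between readings. The chance of at least one PCST is 1 − (1 − r)^6 on post-iv readings alone and 1 − (1 − r)^8 when pooled.

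- r = 2%: 11.4% against 14.9%.
- r = 5%: 26.5% against 33.7%.
- r = 10%: 46.9% against 57.0%.

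For IIB children the window opens at the first iv dose, so this pooling does not arise.

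**The case against.** The any-BRV window is a deliberate choice. It matches the TEAE window in SAP 10.2, and OLB and RxB children are already on BRV when they enter. The variables are secondary and the analysis is descriptive. This stands, and it is why the existing flag should stay.

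The plan also gives readers more help than the percentages alone suggest:

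- The pre-infusion PCST cell sits beside the post-infusion cells for OLB, RxB and IOB subjects. For IIB it helps only from the second infusion.
- The line plots draw one line per child, with PCST values marked.
- There are listings and change-from-Baseline tables. For ECG, "Change from Baseline for ECG parameters will be summarized for all post-Baseline timepoints within each visit".
- For vital signs there is the per-subject PCST table.

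These outputs allow reconstruction by hand. None yields a summary count. Equal counts before and after may be the same child or different children, and change tables show averages. The shift tables in SAP 10.5.2, which set each post-iv result "compared to their pre-iv ECG finding in the same visit", cover the Investigator's ECG grading and not PCST.

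A reader might infer that the pooled count and the per-subject table also affect ECG. SAP 10.5.2 plans neither for ECG, so that part applies to vital signs only. A reader might also infer that every vital-sign and ECG variable is affected. ECG heart rate is not, and low BP largely is not.

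**Conclusion.** The point holds as a presentation weakness that is cheap to repair. As written, an unchanged pre-existing value of the listed variables is PCST after the infusion, and no planned PCST summary separates it from a new one.

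The one-child effect of 16.7 or 8.3 percentage points follows from the planned cell sizes. It assumes that the child's value stays beyond the limit at the time point concerned. The probabilities in the working rest on assumed prevalences and, for the pooled count, on independent readings. They show a range and are not estimates.

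It would be tempting to conclude that the PCST percentages will be substantially inflated, or that the plan conceals pre-existing abnormalities. The documents support neither: they give no prevalence, and the individual data are shown. Nor do they support calling the any-BRV window an error or a breach of Protocol 12.4.1.2, which makes the post-iv against pre-iv comparison optional.

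**What to change.** Keep the any-BRV PCST flag, its listings, and its by-time-point tables including the pre-infusion cells, which are the comparator. Then add:

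1. **Rows for PCST new after iv**, identical in all four subject groups. Count values after the start of the first iv infusion that meet an absolute limit, in the same direction, not met at the SAP 3.4 Baseline. Also count those that meet an existing change-from-Baseline ECG limb whatever the Baseline status. For example, QTc from 445 to 520 ms counts, since 520/445 − 1 = 16.9% exceeds 15%. ECG heart rate keeps its combined rule.
2. **For infusions after the first**, PCST status against the pre-infusion value of the same visit. A single Baseline does not make the per-infusion comparison that Protocol 12.4.1.2 describes.
3. **A split of the vital-sign count** of children with at least one PCST into three lines: pre-iv only; post-iv and already present at Baseline; new after iv. Count each child once, in the last line that applies. Footnote children with a missing Baseline.

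No new data are needed; the cost is a derived flag and some rows. There are drawbacks. The new rows use a different window from the TEAE tables. Both CSR deliveries in SAP 4.3.2 need the same rows. Under 17 years, worsening of a vital sign already PCS at Baseline will show only in the change-from-Baseline tables. A value that fluctuates around a limit may be counted as new.
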